Phase 2 Clinical Protocol BCT-101-US Amendment 1.1, June 2019	MSC-NTF cells (NurOwn®)	Page 5 of 59

STUDY SYNOPSIS

Name of Sponsor	Brainstorm Cell Therapeutics, Ltd. [name] [name]
Investigational Product	NurOwn®: Mesenchymal Stem Cells Secreting Neurotrophic Factors (MSC-NTF cells)
Indication	Progressive Multiple Sclerosis (MS)
Study number	BCT-101-US
Title of Study	A Phase 2, Open-label, Multicenter Study to Evaluate Efficacy and Safety of Repeated Administration of NurOwn® (Autologous Mesenchymal Stem Cells Secreting Neurotrophic Factors; MSC-NTF cells) in Participants with Progressive MS
Protocol Date/Version	June 2019/Amendment 1.1

OBJECTIVES

To determine the safety and efficacy of repeated administration of intrathecal injections (doses) of NurOwn® (MSC-NTF: autologous Mesenchymal Stem Cells [MSC] Secreting Neurotrophic Factors [NTF]) given three times at two monthly intervals to participants with Progressive MS.

Primary:

- To evaluate safety and tolerability of 3 intrathecal (IT) doses of NurOwn® (MSC-NTF cells)

[figure not shown]
Secondary:

- To evaluate the efficacy of NurOwn® using improvement in either Timed 25-foot walk (T25FW) speed or 9-Hole Peg Test (9HPT)
- To evaluate the modulation of cerebrospinal fluid (CSF) and blood biomarkers (neurotrophic factors, neurodegenerative, and inflammatory biomarkers) following NurOwn® transplantation
- To evaluate the efficacy of NurOwn® using:
- The Expanded Disability Status Scale (EDSS).
- The 12 item MS Walking Scale (MSWS-12)
- Physical function (including average daily step count using a wrist wearable sensor)
- Low Contrast Letter Acuity (LCLA)
- Symbol Digit Modalities Test (SDMT)
- MSFC Composite scores

METHODOLOGY

Study Design	This is an open-label study with a single treatment arm involving 20 participants with progressive MS at multiple investigational study sites. After providing informed consent, participants meeting the inclusion and exclusion criteria will be enrolled and 1- 4 weeks later will undergo a bone-marrow aspiration (BMA). The first IT transplantation will be at Visit 3 (Day 0), 6-10 weeks after screening/enrollment visit, with the subsequent transplants at Visit 4 (Week 8) and Visit 5 (Week 16). Following the third and last treatment, participants will be followed for 12 weeks with two additional visits, approximately 6 weeks apart.
---------------------	--

Brainstorm Cell Therapeutics Ltd.	IND#018615	
Phase 2 Clinical Protocol BCT-101-US Amendment 1.1, June 2019	MSC-NTF cells (NurOwn®)	Page 6 of 59

Study Duration	Approximately 38 weeks (up to 10 weeks pre-treatment and 28 weeks post-treatment).
Number of sites	This is a multi-center phase 2 study to be conducted at 5 US Medical Centers.
Treatments	Three NurOwn® (MSC-NTF cells) treatments will be given by intrathecal administration every two months.
Randomization	None
Treatment Duration	
Each subject's participation in the study will last for approximately 38 weeks (9-10 months), consisting of:
 
 • An approximate 10-week pretreatment period during which participants will undergo bone marrow aspiration and baseline evaluations • A 16-week treatment period during which participants will be administered 3 doses of NurOwn® (MSC-NTF cells) at 8-week intervals (Day 0-1, week 8, and week 16), • A 12-week follow-up period
Study Drug and Formulation	Study drug will be supplied in one 5 mL syringe containing 4 mL of NurOwn® (MSC-NTF cells) suspension at a dose of 100-125 x10 ⁶ cells for IT administration.
Dose and Route of Administration	Doses of 100-125 x10 ⁶ NurOwn® (MSC-NTF cells) transplanted intrathecally at visits 3, 4 and 5.
Concomitant Excluded Therapy	Current use of immunosuppressive medication or use of such medication within 6 months of study enrollment (aside from approved B-cell immunotherapy). Alemtuzumab (Lemtrada), Cladribine (NDA submitted), Natalizumab (Tysabri), S1P modulators (Gilenya) pulse intravenous methylprednisolone (IVMP, 1 gram) to treat a relapse within the 6 months prior to study entry or other investigative MS therapies. However, a single dose of IVMP 100 mg as part of the Ocrevus (or Rituxan) infusion protocol q6M is not exclusionary and would be allowed in the study.
SUBJECT POPULATION	
Number of Participants	20 total participants (approximately 4 participants per site)

Brainstorm Cell Therapeutics Ltd.	IND#018615	
Phase 2 Clinical Protocol BCT-101-US Amendment 1.1, June 2019	MSC-NTF cells (NurOwn®)	Page 7 of 59

Major Inclusion Criteria	
 1. Males and females ages 18 to 65 years old, inclusive, at the Screening Visit (Visit 1). 2. Clinical diagnosis of Progressive MS (Primary and Secondary) based on the 2017 revised McDonald Criteria and confirmation by the Investigator that the disease has entered the progressive stage at least 6 months prior to enrollment. 3. No evidence of clinical MS relapse or high dose pulse corticosteroid treatment within 6 months prior to screening 4. Disability status at screening with an Expanded Disability Status Scale (EDSS) 3.0-6.5. 5. Able to walk 25 feet in 60 seconds or less. 6. Stable dose of non-excluded MS Disease Modifying Therapy for at least 6 months prior to Screening Visit (Visit 1).
Major Exclusion Criteria	
 1. Prior stem cell therapy of any kind. 2. Active participation in any other MS interventional study or of unapproved MS investigational therapy within 90 days prior to the Screening Visit (Visit 1). 3. Inability to lie flat for the duration of intrathecal cell transplantation and/or bone marrow aspiration, or inability to tolerate study procedures for any other reason. 4. History of clinically significant autoimmune disease (excluding thyroid disease) that may confound study results, myelodysplastic or myeloproliferative disorder, leukemia or lymphoma, whole body irradiation, hip fracture, or severe scoliosis. 5. Any unstable clinically significant medical condition other than-multiple sclerosis (e.g., within six months of Screening Visit (Visit 1), had myocardial infarction, angina pectoris, and/or congestive heart failure), any clinically significant coagulopathy, treatment with anticoagulants that, in the opinion of the investigator, would compromise the safety of participants. 6. Any history of malignancy within the previous 5 years, except for non-melanoma localized skin cancers (with no evidence of metastasis, significant invasion, or re-occurrence within three years of Screening Visit (Visit 1)). 7. Current use of immunosuppressant medication or use of such medication within 6 months of study enrollment (aside from approved B-cell immunotherapy). 8. Any history of acquired or inherited immune deficiency syndrome. 9. Pregnant women or women currently breastfeeding. 10. Subjects for whom MRI is contraindicated (i.e., have a pacemaker or other metallic implanted device) or are unable to remain in the machine for period of time needed to acquire a scan. 11. Positive test result for Hepatitis B virus (HBV; surface antigen (HBsAg) and antibodies to core antigen (IgG and IgM anti-HBc)), Hepatitis C virus (HCV), Human Immune deficiency Virus (HIV) 1 and 2.
ASSESSMENTS	
Safety	Changes in vital signs and physical examination findings, hematology, blood chemistry, urinalysis, AEs, and changes in concomitant medications. New MRI lesions (new - or newly enlarging – T1 and T2 weighted images will be evaluated for safety).
Efficacy	Efficacy assessments will be based upon: T25FW, 9-HPT, blood and CSF biomarkers, EDSS, MSWS-12, Physical function measured with wearable sensor, LCLA, and SDMT. The efficacy endpoints are further described in the statistical section below.
Biomarkers	Paired CSF samples and serum samples will be collected prior to each intrathecal administration of MSC-NTF cells. CSF and/or blood samples will be evaluated for levels of disease and other relevant biomarkers (such as neurotrophic and inflammatory factors, miRNAs and other relevant cytokines) and their potential relation to efficacy outcomes.

Brainstorm Cell Therapeutics Ltd.	IND#018615	
Phase 2 Clinical Protocol BCT-101-US Amendment 1.1, June 2019	MSC-NTF cells (NurOwn®)	Page 8 of 59

DATA SAFETY MONITORING BOARD		
DSMB	An independent Data Safety Monitoring Board (DSMB) will be established for the study. The DSMB will review key safety and efficacy data (at intervals and as requested) as outlined in the DSMB charter.	
STATISTICAL METHODS AND ANALYSIS		
Sample Size Calculation	No formal sample size calculation is performed. Efficacy and safety data in the 20 participants will provide information to inform the design of a future randomized study.	
Efficacy	
Efficacy analyses will be performed using the modified intent to treat (mITT) and Efficacy Evaluable (EE) populations. The mITT population will be defined as all participants who received at least one treatment and had at least one T25FW or a 9HPT assessment post treatment. The EE population will be defined as a subset of the mITT population that receive all 3 treatments and do not have any important protocol deviations impacting efficacy evaluation. If the EE population is identical or very similar to the mITT population, analyses may only be generated for the mITT population.
 
Efficacy assessments will be based upon, T25FW, 9-HPT, blood and CSF biomarkers, EDSS, MSWS-12, Physical function measured with wearable sensor outputs LCLA and SDMT.
 
Efficacy analyses of continuous data will be based upon change from baseline to each post-baseline timepoint. Baseline will be defined as the last measurement prior to the first treatment.
 
Responder analyses will compare the proportion of responders using various definitions of responders for the different efficacy endpoints.
	
Safety	
All safety analyses will be conducted on the Safety Population, which will be defined as all participants who were enrolled and had at least one transplantation performed.
 
Only observed data will be analyzed and no imputations will be performed for any missing safety data.
 
Safety analysis of continuous data will be based upon change from baseline to each post-baseline timepoint. Baseline will be defined as the last measurement prior to the first treatment.
 
Abnormalities in hematology, blood chemistry, MRI and electrocardiogram (ECG) assessment will be summarized.
	
Biomarkers	Paired CSF and blood samples will be analyzed for the disease relevant biomarkers and their relationship to efficacy outcomes. In addition, relationships between neurotrophic factors, inflammatory markers, miRNAs and clinical outcomes will be evaluated to determine if any biomarkers can be predictive of treatment outcome.	

Brainstorm Cell Therapeutics Ltd. Phase 2 Clinical Protocol BCT-101-US Amendment 1.1, June 2019	IND#018615 MSC-NTF cells (NurOwn®)	Page 9 of 59
---	---------------------------------------	--------------

TABLE OF CONTENTS

Description	Page
CLINICAL STUDY PROTOCOL	1
CLINICAL STUDY PROTOCOL [BCT-101-US]	2
PROTOCOL APPROVAL	3
STUDY SYNOPSIS	5
ABBREVIATIONS	14
1. INTRODUCTION	17
1.1. STUDY OBJECTIVES	19
1.1.1. Primary objectives	19
1.1.2. Secondary Objectives	19
2. INVESTIGATIONAL PLAN	20
2.1. OVERALL STUDY DESIGN AND PLAN	20
2.2. STUDY SCHEMATIC	21
2.3. TREATMENT PLAN	22
2.3.1. Bone Marrow aspiration procedure	22
2.3.2. Intrathecal Transplant Procedure	22
2.4. DURATION OF STUDY	23
2.5. DISCUSSION OF DOSE	23
2.6. DISCUSSION OF STUDY DESIGN, INCLUDING CHOICE OF CONTROL GROUP	23
3. PATIENT POPULATION	23
3.1. INCLUSION CRITERIA	24
3.2. EXCLUSION CRITERIA	24
4. STUDY ASSESSMENTS	25
4.1. CSF AND BLOOD COLLECTION FOR ASSESSMENTS OF BIOMARKERS	26
4.2. MRI	26
4.3. WEARABLE SENSOR DEVICE	26
4.4. CLINICAL LABORATORY SAFETY TESTS	26
4.5. PHYSICAL EXAMINATIONS, VITAL SIGNS, AND ELECTROCARDIOGRAMS	27

Brainstorm Cell Therapeutics Ltd.	IND#018615	
Phase 2 Clinical Protocol BCT-101-US Amendment 1.1, June 2019	MSC-NTF cells (NurOwn®)	Page 10 of 59

4.6.	PRE-TRANSPLANTATION VISITS.....	27
4.6.1.	Visit 1: Screening Visit.....	27
4.6.2.	Visit 2: Bone Marrow Aspiration Visit (Week -5, - -6)	28
4.7.	TRANSPLANTATION VISITS	29
4.7.1.	Visit 3 (T1): 1st Cell Transplantation (Day 0- up to Day 1).....	29

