6. PRIOR AND CONCOMITANT THERAPY

6.1. PRIOR THERAPY

Participants who received prior cell therapy of any kind will be excluded from the study (see Section 3.2).

Study participants who begin an excluded medication during the study period will be discontinued from treatment. In order to minimize the amount and impact of missing data, study investigators will make all reasonable efforts to collect key efficacy and safety data on participants who discontinue treatment or discontinue from the study.

All medications taken prior to the first transplantation will be recorded as Prior medications.

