6.2. CONCOMITANT AND EXCLUDED THERAPY

Concomitant medications are those given to the subject during or after the first transplantation. All concomitant medications will be recorded.

Brainstorm Cell Therapeutics Ltd.	IND#018615	
Phase 2 Clinical Protocol BCT-101-US Amendment 1.1, June 2019	MSC-NTF cells (NurOwn®)	Page 36 of 59

Current use of immunosuppressive medication or use of such medication within 6 months of study enrollment (aside from approved B-cell immunotherapy) and anticoagulation therapy are exclusionary.

Alemtuzumab (Lemtrada), Cladribine (NDA submitted), Natalizumab (Tysabri), S1P modulators (such as Gilenya) high dose pulse intravenous methylprednisolone (IVMP, 1 gram) to treat a relapse within the 6 months prior to study entry or other investigative MS therapies are exclusionary due to safety considerations. However, a single dose of IVMP 100 mg as part of the Ocrevus (or Rituxan) infusion protocol q6M is not exclusionary and would be allowed in the study.

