7.7. Prior and Concomitant Medications

All medications (e.g., both prior and concomitant) will be coded with respect to the Anatomical Therapeutic Chemical (ATC) drug classification coding system and the data summarized by level 2 and PT. Therefore, all possible ATC codes for a given medication by the WHODD Version September, 2018 will be displayed.

The displays of medications will be performed without any regard to the indication the medication was taken for.

Separate Tables will display prior medications and CMs using the Safety Population.

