9.2. Analysis of Primary Efficacy Endpoint

The primary objective and endpoints in the study are assessments of safety. The secondary objective and endpoints are assessments of efficacy.

The first secondary endpoint is considered the primary efficacy endpoint for this study.

Efficacy analyses will be performed using the modified mITT and EE populations. If mITT and EE populations are the same then, all efficacy analysis will be performed using mITT population only.

The primary efficacy endpoint will be a responder analysis to see if subjects improve in walking speed as measured by time to complete T25FW (ft/sec.) or improve in finger (fine manual) dexterity as measured by time to complete the 9-HPT (sec.)

A subject will be defined as a responder to study drug if their T25FW walking speed or 9-HPT improves by 25% or more between baseline and Week 28. An improvement of 25% is considered clinically meaningful for MS patients^{4,6}.

All deaths related to disease progression or treatment will be defined as non-responders.

The T25FW, 9-HPT, LCLA and SDMT are part of the current Multiple Sclerosis Functional Composite (MSFC) and described in Additional detail in [the BCT-101-US Protocol, Sections 15.2.1, 15.2.2, 15.2.3, 15.2.6, and 15.2.7](#) in Appendix 1.

The T25FW is a quantitative mobility and leg function performance test based on a timed 25 foot-walk. It is the first component of the MSFC to be administered at each visit. The subject is directed to one end of a clearly marked 25-foot course and is instructed to walk 25 feet as quickly as possible, but safely. The time is calculated from the initiation of the instruction to start and ends when the subject has reached the 25-foot mark. The task is immediately administered again by having the subject walk back the same distance. T25FW score is the average in seconds of the two successive trials. Subjects may use assistive devices when doing this task. An increase in speed for T25FW is considered an improvement.

The MSFC uses a z-score transformation which will be used in assessing the changes in the MSFC.

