9.5.1. Sensitivity Analyses of the Primary Efficacy Results

Select sensitivity analyses may be performed on the primary efficacy results if there is missing data or protocol deviations that can impact results.

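### No rule covers permitted MS or symptomatic therapy started, switched or increased after screening, so a 25% gain that follows is counted as response to NurOwn

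*Protocol*

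**What the plan says.** **Entry.** Criterion 6 (Protocol Synopsis and 3.1) requires "Stable dose of non-excluded MS Disease Modifying Therapy for at least 6 months prior to Screening Visit (Visit 1"). Neither place sets a condition after that visit.

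**On study.** Protocol 6.1 has the only rule on a new MS drug: "Study participants who begin an excluded medication during the study period will be discontinued from treatment". The same section asks sites to go on collecting efficacy data on such participants. Approved B-cell therapy is outside the exclusions. Protocol 6.2 adds that "a single dose of IVMP 100 mg as part of the Ocrevus (or Rituxan) infusion protocol q6M is not exclusionary".

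**Scoring.** SAP 9.2 states: "A subject will be defined as a responder to study drug if their T25FW walking speed or 9-HPT improves by 25% or more", measured from baseline to Week 28. Baseline is the last assessment before the first treatment at Visit 3 (SAP 6.6). The one event that overrides the rule is a death related to progression or treatment.

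**Other analyses.** SAP 9.5.1 offers: "Select sensitivity analyses may be performed on the primary efficacy results if there is missing data or protocol deviations that can impact results". The Efficacy Evaluable set removes participants who miss a dose or have important deviations (SAP 6.5.3). SAP Appendix I, section 2, drops key efficacy analysis on that set. SAP 9.4 plans no subgroups.

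**Medication displays.** SAP 7.7 tabulates medications by drug class and preferred term, and says: "The displays of medications will be performed without any regard to the indication the medication was taken for".

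**The concern.** Criterion 6 implies that a recent change in MS therapy could disturb the outcome. The same reasoning applies to a change made during follow-up, but there the plan is silent. With a single arm, a gain that follows another treatment cannot be separated from a NurOwn effect unless the analysis identifies it.

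The responder proportion is the primary efficacy endpoint. It is to be tested at two-sided 0.05 against matched historical patients (SAP 9.1), and the study's data are meant to inform a randomized trial (SAP 4.3). If some responders had also changed therapy, a reader of the planned tables would see one pooled percentage with no way to judge how much of it depends on them.

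**Working it through.** **1. The time window.** SAP section 2 gives total observation as 34-38 weeks. The protocol synopsis puts the first treatment "6-10 weeks after screening/enrollment visit", with 28 weeks after it: 6 + 28 = 34 and 10 + 28 = 38, so the stated figure is reproduced. That is the period without a stability rule. Response is scored only over the last 28 weeks. The stretch before baseline is 6/34 = 18% to 10/38 = 26% of the total. A change made there matters only for an effect that appears after Visit 3, because an effect complete by then is already in the baseline.

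**2. One case followed through the plan.** Suppose a participant starts a permitted MS drug between Visits 3 and 4 and gains 25% at Week 28.
- Criterion 6: met, since it looks back from screening.
- Protocol 6.1: not triggered, since the drug is not excluded.
- SAP 9.2: counted as a responder.
- SAP 6.5.3: no stated rule was broken, and important deviations are not defined, so removal is not assured. Appendix I drops the key analysis on that set in any case.
- SAP 9.5.1: optional, and tied to missing data or deviations.
- SAP 7.7: the drug appears by class and name, but no table shows when it was started or links it to response.

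If the same drug is started between Visits 1 and 3 and continued, Appendix I 3.4 defines it as a prior medication. It is then tabulated with therapy that had been stable for years.

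**3. Size per participant.** 1/20 = 5 percentage points.

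**4. Illustration on assumed values.** The documents give no background response rate (p0), no number of participants changing therapy (k) and no response probability after a change (q). Assume that NurOwn has no effect, that k of 20 respond with probability q and that the other 20 - k respond with probability p0. The expected rate is (k·q + (20 - k)·p0)/20. For k = 4 and p0 = 10% this is (1 + 1.6)/20 = 13% at q = 25% and (2 + 1.6)/20 = 18% at q = 50%.

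The cut-off r is the smallest count whose exact upper tail under Binomial(20, p0) is at most 0.025. The false-positive probability is P(X + Y ≥ r), with X ~ Binomial(k, q) and Y ~ Binomial(20 - k, p0). Ranges run from q = 25% to q = 50%.

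| p0 | r | k = 0 | k = 2 | k = 4 |
|---|---|---|---|---|
| 5% | 4 | 1.6% | 4.2%-8.8% | 9.0%-28.5% |
| 10% | 6 | 1.1% | 2.0%-4.0% | 3.4%-11.3% |
| 15% | 7 | 2.2% | 3.0%-5.4% | 4.0%-11.6% |

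These figures treat p0 as a fixed rate, which simplifies the planned comparison with matched patients. They also assume that the change helps.

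**The case against.** The strongest reply is that the effect may be small and its direction unknown.

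- **Plausibility.** The protocol introduction says progressive MS lacks effective therapy and that approved drugs work best before the progressive phase. A newly started disease-modifying drug may rarely produce a 25% gain. This stands as a limit on size. It has less force for symptomatic drugs. Criterion 6 never covered those, even at entry; they matter here because the endpoints are walking speed and manual dexterity.
- **Direction.** A reader might infer that the error can only favour NurOwn. The documents do not support that. Therapy can be stopped, or escalated because a participant is worsening. Nothing says the CLIMB registry patients were held on stable therapy either. Their change over 1 to 2 years is scaled linearly to 28 weeks (Appendix I, section 5), which keeps 28/104 = 27% to 28/52 = 54% of any observed gain. They also had longer in which to change therapy. The net effect on the contrast is therefore open, and cancellation cannot be assumed.
- **Visibility.** A reader might infer that such drugs are hidden from the tables. They are not. SAP 7.7 shows classes and names, SAP 6.1 provides individual listings, and Protocol Table 1 has medications reviewed at every visit. What is missing is a display of new or changed MS-related therapy set against response.
- **Choice of estimand.** Counting everyone as observed is a legitimate choice, and scoring changers as failures is another. Applied to the trial arm alone, the second would bias the contrast downward. This stands, and it is why the fix reports both.
- **Priority.** Safety is the primary objective and the study has no sample-size calculation. That lowers the urgency.

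**Conclusion.** The point holds as a gap in pre-specification. Stability of MS therapy is required only up to screening, and the SAP does not say how a later change in permitted or symptomatic therapy is handled in the responder analysis. The rule in SAP 9.2, followed exactly, credits NurOwn with a 25% gain that follows such a change.

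The change alone is not scored as response: the participant must also reach the threshold between Visit 3 and Week 28.

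The firm figure is 5 percentage points per affected participant, with a denominator of 20. The false-positive figures rest wholly on assumed rates; they show that a handful of participants could matter, not that they will. This is a worthwhile and inexpensive improvement, and it does not invalidate the study.

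**What to change.** 1. **SAP 9.2 and 9.5.1.** Pre-specify a responder analysis that scores a participant as a non-responder, from the date of change, if between Visit 1 and the assessment they start, switch or increase an MS disease-modifying therapy or a listed symptomatic drug for walking, spasticity or hand function. Report it beside the as-observed responder rate.
2. **Drug list.** Fix it before the outcome data are reviewed. This needs care because SAP 5.1 allows efficacy to be analysed while the study is running.
3. **Comparators.** Apply the same rule to the CLIMB patients if their medication data allow it. If not, state that limit next to the comparison.
4. **SAP 7.7.** Add a by-participant table of MS-related therapy started or changed after Visit 1, with dates relative to visits and responder status.
5. **Protocol.** Have the sponsor state whether the stability condition continues after screening. That is a clinical decision, and none is proposed here.

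The cost is SAP wording, one extra analysis and one table from the existing medication log. The responder rate in the added analysis may be slightly lower, and a true responder who changed therapy would be scored there as a failure.
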